3.1 Primary Endpoints

As this is an exploratory study, there are no primary endpoints.

3.2 Secondary Endpoints

As this is an exploratory study, there are no secondary endpoints.

3.3 Efficacy Endpoints

The efficacy endpoints include the following:

- Fluorescein staining (Ora Calibra[®] scale) at Visits 3, 4 (pre-CAE, post-CAE, and pre- to post-CAE), and 5 (pre-CAE, post-CAE, and pre- to post-CAE) in the following regions: central, superior, inferior, temporal, nasal, corneal sum, conjunctival sum, and total eye score
- Ocular discomfort and dry eye symptoms at Visits 3, 4 (pre-CAE, post-CAE, and pre- to post-CAE), and 5 (pre-CAE, post-CAE, and pre- to post-CAE)
- Lissamine green staining (Ora Calibra® scale) at Visits 3, 4 (pre- CAE, post-CAE, and pre- to post-CAE), and 5 (pre-CAE, post- CAE, and pre- to post-CAE) in the following regions: central, superior, inferior, temporal, nasal, corneal sum, conjunctival sum, and total eye score

- Tear film break-up time (TFBUT) at Visits 3, 4 (pre-CAE, post-CAE, and pre- to post-CAE), and 5
 (pre-CAE, post-CAE, and pre- to post- CAE)
- Conjunctival Redness at Visits 3, 4 (pre-CAE, post-CAE, and pre- to post-CAE), and 5 (pre-CAE, post-CAE, and pre- to post- CAE), and mean change from baseline Visit 2 (Day 1) pre-CAE to Visit 5 (Day 84) pre-CAE
- Ocular Surface Disease Index (OSDI) at Visits 3, 4, and 5 (pre-CAE)
- Schirmer's test at Visit 3, 4, and 5
- Ocular discomfort during CAE at Visits 4 and 5
- Daily Diary Symptom Score

3.4 Safety Endpoints

The safety endpoints include the following:

- Visual acuity
- Slit-lamp evaluation
- Adverse event query
- Intraocular pressure
- Undilated fundoscopy
- Drop comfort assessment after randomization at Visit 2, 3, 4, and 5

3.5 Statistical Hypotheses

The clinical hypotheses for this study is that IC265 Ophthalmic Solution 1% twice daily (BID) is superior to its vehicle (BID) for the efficacy endpoints.

4. Study Design and Procedures

4.1 General Study Design

This is a Phase 2, single-center, double-masked, randomized, placebo-controlled clinical study. Subjects will be randomized to one of the following treatment arms at Visit 2 (Day 1):

- IC265 Ophthalmic Solution 1%: 1 drop BID bilaterally (N=~20)
- Placebo Ophthalmic Solution (Vehicle): 1 drop BID bilaterally (N=~20)

Approximately 40 subjects will be randomly assigned to one of the two groups (1:1) to receive either IC265 Ophthalmic Solution 1% or placebo solution as topical ophthalmic drops administered bilaterally BID for 12 weeks. Subjects, Sponsor, Contract Research Organization (CRO), and site personnel will be masked to treatment assignment.

During the 14-day study run-in period prior to randomization, all subjects will receive Placebo Ophthalmic Solution (Vehicle) bilaterally BID.

During the screening period, two 90-minute exposures to the CAE will be conducted to ascertain eligibility to enter the study at Visit 1 (Day -14 \pm 2) and Visit 2 (Day 1). Subjects who qualify after the initial screening visit will enter the run-in phase, where they will self-administer vehicle BID for approximately 14 days. Those who qualify at Visit 2 (Day 1) will be randomized to receive study drug in a double-masked fashion for 84 days. Subjects will self-administer drops BID and will complete Daily diary symptom score assessments as instructed. The CAE exposure will occur at Visit 1 (Day -14 \pm 2), Visit 2 (Day 1), Visit 3 (Day 15 \pm 2), Visit 4 (Day 43 \pm 2), and Visit 5 (Day 85 \pm 4), with Pre-CAE, during CAE and Post-CAE assessments of ocular signs and symptoms. Study drug will be discontinued at Visit 5. Subjects will exit from the study at this visit.

Study visits will be referred to in all tables and listings as the scheduled visit name and planned study day corresponding to the visit to enable reviewers to understand the assessment timing without referring to the protocol visit schedule.

4.2 Schedule of Visits and Assessments

The schedule of visits and assessments is provided Appendix 1.

4.3 Study Treatments

IC265 Ophthalmic Solution will be formulated as a sterile, non-preserved solution around pH 6 for topical ophthalmic administration and is intended for clinical use. The study drug will be supplied in blow-fill seal ampoules, which allow for product administration directly to the eye. Each ampoule will contain a nominal volume of 0.27 mL.

The excipients which will be used to manufacture IC265 Ophthalmic Solution will be standard excipients for use in ophthalmic solutions that comply with their respective USP / EP monographs.

The placebo for IC265 Ophthalmic Solution contains all the same excipients used in the active formulation without the API.

5. Sample Size

Approximately 80 subjects will be screened to enroll 40 subjects (20 subjects in each group). This is a Phase 2 study for which no formal sample size calculation has been performed. The sample size chosen was not based on statistical considerations, but is based on historical experience.

6. Data Preparation

6.1 Input Data

Study data will primarily be recorded on the electronic Case Report Forms (eCRFs) supplied by SDC using iMedNet and SDC Capture™.

When all prerequisites for database lock have been met, the database will be locked. Following database lock, approval will be obtained from the Sponsor to unmask the study. Any changes to the database after data have been locked can only be made with the approval of the Sponsor in consultation with SDC.

Final analysis will be carried out after the following have occurred:

- Database lock has occurred.
- Analysis populations have been determined.
- Randomized treatment codes have been unmasked.

6.2 Output Data

Data from EDC will be transferred to SDC Biostatistics. Data will then be mapped to analysis datasets. Both raw and analysis data will be used to create the subject listings, while all tables and figures will be based on the analysis data.

7. Analysis Populations

7.1 Intent-to-Treat Population

The Intent-to-Treat (ITT) Population includes all randomized subjects. All efficacy analyses will be performed on the ITT Population, and subjects will be analyzed as randomized.

7.2 Safety Population

The Safety Population includes all randomized subjects who receive at least one dose of the investigational product. The subjects will be analyzed as treated. All safety analyses will be based on the Safety Population.

8. General Statistical Considerations

8.1 Unit of Analysis

Safety endpoints will be analyzed for both eyes. For efficacy endpoints, the unit of analysis will be the study eye, or the "worst eye," as defined by the following:

Study Eye: Eyes are eligible for analysis if they meet all of the inclusion criteria. In the case that both eyes are eligible for analysis, the study eye will be the eye with the worst (higher) total corneal fluorescein staining, based on the sum of the inferior, superior, and central regions, at baseline (Visit 2) pre-CAE. If the total corneal staining is the same in both eyes, then the right eye will be selected as the study eye.

The non-study eye will be referred to as the fellow eye. Fellow eye safety summaries will also be presented as appropriate. Additionally, non-ocular AEs and medical history will be presented at the subject level.

8.2 Missing or Inconclusive Data Handling

8.2.1 MISSING EFFICACY ASSESSMENTS

No imputation will be used for efficacy endpoints.

8.2.2 MISSING SAFETY ASSESSMENTS

No imputation will be used for safety endpoints.

8.3 Definition of Baseline

Baseline measures are defined as the last non-missing measure prior to the initiation of randomized study treatment, usually at Visit 2 (Day 1).

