8.4 Data Analysis Conventions

All data analysis will be performed by SDC. Statistical programming and analyses will be performed using SAS® Version 9.4 or higher. Output will be provided in rich text format (RTF) for tables and portable document format (PDF) for tables, listings, and figures using landscape orientation.

Summaries for continuous and ordinal variables will include the number of observations (n), arithmetic mean, standard deviation (SD), median, minimum, and maximum. Minima and maxima will be reported with the same precision as the raw values; means and medians will be presented to one additional decimal place than reported in the raw values. Standard deviations will be presented to two additional decimal places than reported in the raw values. Summaries for discrete variables will include counts and percentages. All percentages will be rounded to one decimal place (i.e., XX.X%). Differences between active treatment and placebo will be calculated as, Active – Placebo, and change from baseline will be calculated as, Follow-up Visit – Baseline.

Unless otherwise specified, summaries will be presented by treatment group and, where appropriate, visit. Listings will be presented by subject number, treatment group, visit, time point, and parameter as applicable based on all randomized subjects unless otherwise specified.

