14.3 Slit-Lamp Biomicroscopy

A slit-lamp biomicroscopy examination of the cornea, conjunctiva, anterior chamber, iris, lens, and eyelid will be performed at each visit. The results will be graded as normal, abnormal not clinically significant (NCS), or abnormal clinically significant (CS).

The results will be summarized using counts and percentages for each treatment group and for all actively treated subjects at each visit for each eye (study eye and fellow eye). Percentages will be based on the number of subjects in each treatment group with responses. Shift tables for the slit-lamp biomicroscopy parameters will also be provided comparing each follow-up visit to baseline. A subject listing of the slit-lamp biomicroscopy parameters will also be produced.

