| 14.1.5.1 | Study Drug Compliance | Intent-to-Treat Population |
| 14.1.5.2 | Overall Study Drug Exposure | Safety Population |
| 14.2.1.1 | Ora Calibra Corneal and Conjunctival Fluorescein Staining in Study Eye by Visit | Intent-to-Treat Population |
| 14.2.1.2 | Ora Calibra Ocular Discomfort & 4-Symptoms Questionnaire in Study Eye by Visit | Intent-to-Treat Population |

| Table Number | Title | Population |
|--------------|---|-------------------------------|
| 14.2.1.3 | Ora Calibra Ocular Discomfort Scale during the CAE in Study Eye by Visit | Intent-to-Treat Population |
| 14.2.1.4 | Ora Calibra Corneal and Conjunctival Lissamine Green Staining in Study Eye by Visit | Intent-to-Treat Population |
| 14.2.1.5 | Tear Film Break-Up Time (TFBUT) in Study Eye by Visit | Intent-to-Treat Population |
| 14.2.1.6 | Ora Calibra Conjunctival Redness in Study Eye by Visit | Intent-to-Treat Population |
| 14.2.1.7 | Ocular Surface Disease Index (OSDI) by Visit | Intent-to-Treat Population |
| 14.2.1.8 | Unanesthetized Schirmer's Test in Study Eye by Visit | Intent-to-Treat Population |
| 14.2.1.9 | Daily Diary Symptom Score | Intent-to-Treat Population |
| 14.3.1.1 | Overall Summary of Adverse Events | Safety Population |
| 14.3.1.2 | Ocular Treatment-Emergent Adverse Events by System Organ Class and Preferred Term | Safety Population |
| 14.3.1.3 | Non-Ocular Treatment-Emergent Adverse Events by System Organ Class and Preferred Term | Safety Population |
| 14.3.1.4 | Ocular Treatment-Related Treatment-Emergent Adverse Events by System Organ Class and Preferred Term | Safety Population |
| 14.3.1.5 | Non-Ocular Treatment-Related Treatment-Emergent Adverse Events by System Organ Class and Preferred Term | Safety Population |
| 14.3.1.6 | Serious Treatment-Emergent Adverse Events by System Organ Class and Preferred Term | Safety Population |
| 14.3.2 | Visual Acuity (logMAR) by Visit | Safety Population |
| 14.3.3.1 | Slit Lamp Biomicroscopy Results by Visit | Safety Population |
| 14.3.3.2 | Shifts in Slit Lamp Biomicroscopy from Baseline to Each Post-Baseline Visit | Safety Population |
| 14.3.4.1 | Undilated Fundus Exam Results by Visit | Safety Population |
| 14.3.4.2 | Shifts in Undilated Fundus Exam Results from Baseline to Each Post-Baseline Visit | Safety Population |

| Table Number | Title | Population |
|--------------|---|-------------------|
| 14.3.5 | Intraocular Pressure by Visit | Safety Population |

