23.1 Appendix 1: Schedule of Visits and Measurements

| Procedure | | Visit 1 Day -14 ± 2 | | Visit 2 Day 1 | | Visit 3 Day 15 ± 2 | | Day 29 ± 2 | Visit 4 Day 43 ± 2 | | Day 64 ± 2 | Visit 5 Day 85 ± 4/Early Termination | |
|---|------------------|------------------------|---|------------------|---------------|-----------------------|--------------|---------------|-----------------------|--------------|---------------|--|----------|
| | Pre- CAE | Post - CAE | | Post- CAE | Phone Call | | Post- CAE | Phone Call | ı | Post- CAE | Phone Call | Pre-CAE | Post-CAE |
| Informed Consent / HIPAA | X | | | | | | | | | | | | |
| Medical / Medication History and Demographic | X | | | | | | | | | | | | |
| Run-in Collection | | | X | | | | | | | | | | |
| Study drug Collection | | | | | | X | | | X | | | X | |
| Eyecup Phone and/or Diary Collection | | | X | | | X | | | X | | | X | |
| Medical / Medication History Update | | | X | | | Х | | | X | | | X | |
| Adverse Event Query | X | | X | | Х | Х | | X | X | | X | X | |
| Pregnancy Test | \mathbf{X}^{1} | | | | | | | | | | | \mathbf{X}^{1} | |
| Physical Exam (HEENT) | | | X | | | | | | | | | | |
| Ora Calibra™ Ocular Discomfort & 4-Symptom Questionnaire | Х | Х | X | Х | | X | X | | X | X | | X | Х |
| OSDI [©] Questionnaire | X | | X | | | X | | | X | | | X | |
| Visual Analog Scale (VAS) | X | | X | | | X | | | X | | | X | |
| y (Visual Acuity (ETDRS) | X | | X | | | X | | | X | | | X | |
| Review of Qualification Criteria | X | X | X | X | | | | | | | | | |
| Slit-lamp Biomicroscopy | X | X | X | X | | X | X | | X | Х | | X | X |

| TFBUT | X | X | X | X | | X | X | X | X | X | X |
|--|----------|-------|---|-------|---|-------|---|-------|---|-------|---|
| Fluorescein Staining | X | X | X | X | | X | X | X | X | X | X |
| Lissamine Green Staining | X | X | X | X | | X | X | X | X | X | X |
| Conjunctival Redness | X | X | X | X | | X | X | X | X | X | X |
| CAE® Exposure | 2 | X | | X | | X | | X | | X | |
| Ora Calibra™ Ocular Discomfort Scale | X | X^2 | |
| Digital Photography* | X | X | X | X | | X | X | X | X | X | X |
| Unanesthetized Schirmer's Test | X | | X | | | X | | X | | X | |
| Intraocular Pressure | | X | | | | | | | | | X |
| Undilated Fundus Exam | | X | | | | | | | | | X |
| Run-in Article Dispensation | | Х | | | | | | | | | |
| Run-in Instillation | | X | | | | | | | | | |
| Randomization | | | | X | | | | | | | |
| Randomized Study Drug Instillation | | | | X | | | X | | X | | |

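### SAP 8.3 applied literally takes the Visit 2 post-CAE slit-lamp grade as the single baseline, and nothing in SAP 14.3 or Table 14.3.3.2 matches follow-up examinations to it by CAE time point

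*SAP*

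**What the plan says.** SAP 8.3 gives one baseline rule for all measures: "Baseline measures are defined as the last non-missing measure prior to the initiation of randomized study treatment, usually at Visit 2 (Day 1"). Protocol 10.4.1 has the same rule. Neither mentions the CAE.

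SAP 14.3 describes the slit-lamp data as one examination per visit: "A slit-lamp biomicroscopy examination of the cornea, conjunctiva, anterior chamber, iris, lens, and eyelid will be performed at each visit". Each structure is graded normal, abnormal NCS or abnormal CS. On change from baseline it says: "Shift tables for the slit-lamp biomicroscopy parameters will also be provided comparing each follow-up visit to baseline". The table list in SAP Section 20 gives Table 14.3.3.2 the title "Shifts in Slit Lamp Biomicroscopy from Baseline to Each Post-Baseline Visit". None of these names a CAE time point.

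The schedule in SAP 23.1 marks slit lamp twice, pre-CAE and post-CAE, at every visit from 1 to 5.

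On layout, SAP 8.4 says that, apart from specified exceptions, "summaries will be presented by treatment group and, where appropriate, visit", whereas for listings it says: "Listings will be presented by subject number, treatment group, visit, time point, and parameter". In SAP 13.1.6, the OSDI section, one sentence says that categorical safety assessments are tabulated by treatment and, as applicable, by time point.

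Two places in the SAP attach pre-CAE to the word baseline: study-eye selection (8.1) and the conjunctival redness change from Visit 2 to Visit 5 (3.3).

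**The concern.** The CAE is a 90-minute stress on the ocular surface, so grades before and after it describe different conditions. A shift table is meaningful only if both examinations are made under the same condition. The written baseline rule does not secure that for slit lamp.

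SAP Section 1 records that the study was terminated because of epithelial haziness, and SAP Section 17 replaces testing with descriptive statistics. Readers will therefore look at the corneal rows of Table 14.3.3.2, the planned within-subject summary of slit-lamp change. If those rows set a pre-CAE follow-up grade against a post-CAE baseline grade, they can understate new findings or suggest recovery that did not occur.

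**Working it through.** The plan gives no figure to reproduce. The check applies the SAP 8.3 rule to the order of examinations.

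**Step 1: which grade does the rule select?** Protocol 8.3.1 asks for procedures in the listed order. Protocol 8.3.3 lists, for Visit 2, slit lamp, then the CAE, then slit lamp again, then randomization and the supervised first dose. The slit-lamp examinations before that dose are:

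Visit 1 pre-CAE → Visit 1 post-CAE → Visit 2 pre-CAE → Visit 2 post-CAE → first dose.

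The latest of the four is Visit 2 post-CAE. The Visit 2 pre-CAE grade is selected only if the post-CAE grade is missing.

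**Step 2: does this survive the version gap?** The supplied protocol is Version 1.0; the SAP is written for Version 3.0. The SAP's own text supports the same order. SAP 4.1 states: "Those who qualify at Visit 2 (Day 1) will be randomized to receive study drug in a double-masked fashion for 84 days". In SAP 23.1 the row "Review of Qualification Criteria" is marked post-CAE as well as pre-CAE at Visit 2, and randomization and instillation stand in the Visit 2 post-CAE column.

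**Step 3: how many comparisons are mismatched?** Visits 3, 4 and 5 each have one pre-CAE and one post-CAE examination: 3 × 2 = 6. If both are shown, as SAP 13.1.6 suggests, against the single baseline from Step 1:

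- post-CAE follow-up against post-CAE baseline: 3 matched
- pre-CAE follow-up against post-CAE baseline: 3 mismatched

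So 3 of 6 are mismatched. If only post-CAE follow-up were tabulated, 0 of 3 would be.

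**Step 4: what does a mismatch do?** Take a cornea graded normal at Visit 2 pre-CAE.

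| Visit 2 post-CAE | Follow-up pre-CAE | Matched pre-to-pre shift | Literal post-to-pre shift |
|---|---|---|---|
| Normal | NCS | Normal to NCS | Normal to NCS (same) |
| NCS | NCS | Normal to NCS | NCS to NCS (new finding hidden) |
| NCS | Normal | Normal to normal | NCS to normal (false improvement) |
| NCS | CS | Normal to CS | NCS to CS (still seen as worsening) |

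Rows 2 and 3 are the errors.

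**Step 5: does it reach other measures?** The SAP compares six measures with baseline. OSDI and visual acuity are scheduled pre-CAE only. IOP and fundoscopy are scheduled post-CAE only. Redness is taken at both time points, but its change is specified as pre-CAE to pre-CAE. Slit lamp alone has two time points and none named.

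**The case against.** The best reply is that the SAP, read as a whole, points to matched time points. SAP 3.3 contains its only explicit pairing, for redness, and that is pre-CAE to pre-CAE. SAP 8.1 also attaches a time point to baseline. SAP 8.4 allows for exceptions, and the sentence in 13.1.6 can be read as one, since slit lamp is a categorical safety assessment. A competent programmer might well match time points unprompted. This stands as evidence of probable intent. It does not close the gap: 13.1.6 can split the follow-up results, but it sets no baseline for each part, and 8.3 then supplies the same post-CAE value to both.

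Three stronger readings are tempting, and the documents do not support them.

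- A reader might infer that 8.3 contradicts 8.1 and 3.3. It does not: both are compatible with a baseline that exists per time point.
- A reader might infer that every shift is mismatched, 3 of 3. That requires only pre-CAE follow-up to be tabulated, which no passage says and 13.1.6 makes unlikely.
- A reader might want a number of hidden corneal findings. Entry requires at least a 1-point rise in inferior fluorescein staining after the CAE, which makes a changed corneal grade plausible, but staining is a separate scale. Entry also requires a corneal staining sum of at least 4, so many corneas might already be graded abnormal pre-CAE, which would shrink the problem. Among eyes normal at Visit 2 pre-CAE and abnormal NCS at a pre-CAE follow-up, the hidden share is the share already abnormal at Visit 2 post-CAE. The documents place that nowhere between 0 and 100%.

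It is also fair to say that the corneal signal does not depend on this table. Haziness events are reported in the adverse event tables, and Protocol 9.1 requires clinically relevant deterioration to be recorded as an adverse event.

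**Conclusion.** The point holds as a minor defect in a stated rule. Applied as written, SAP 8.3 selects the Visit 2 post-CAE slit-lamp grade. With both follow-up time points tabulated, 3 of 6 comparisons in Table 14.3.3.2 cross CAE conditions. This rests on two assumptions: that the rule is programmed literally, and that the procedure order of protocol Version 1.0 carries over to Version 3.0, as the SAP's own schedule indicates.

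The effect is confined to Table 14.3.3.2. By-visit slit-lamp counts, listings and adverse event tables would still show a corneal finding, and no efficacy table is affected. A reader might infer a bias between arms at baseline; none is expected, because both Visit 2 grades precede randomized treatment. No count of affected eyes is claimed.

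**What to change.** In SAP 8.3, define baseline by matching CAE time point: for pre-CAE results, the last available pre-CAE value before the first randomized dose; for post-CAE results, the last available post-CAE value before that dose. In SAP 14.3, acknowledge two examinations per visit, and in Table 14.3.3.2 show pre-to-pre and post-to-post shifts in separate panels. Moving the time-point sentence from 13.1.6 to the safety section would make its scope clear.

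The cost is a short paragraph of SAP text, a time-point key in the baseline derivation and one extra table panel. No new data are needed.

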8.4 Data Analysis Conventions

All data analysis will be performed by SDC. Statistical programming and analyses will be performed using SAS® Version 9.4 or higher. Output will be provided in rich text format (RTF) for tables and portable document format (PDF) for tables, listings, and figures using landscape orientation.

Summaries for continuous and ordinal variables will include the number of observations (n), arithmetic mean, standard deviation (SD), median, minimum, and maximum. Minima and maxima will be reported with the same precision as the raw values; means and medians will be presented to one additional decimal place than reported in the raw values. Standard deviations will be presented to two additional decimal places than reported in the raw values. Summaries for discrete variables will include counts and percentages. All percentages will be rounded to one decimal place (i.e., XX.X%). Differences between active treatment and placebo will be calculated as, Active – Placebo, and change from baseline will be calculated as, Follow-up Visit – Baseline.

Unless otherwise specified, summaries will be presented by treatment group and, where appropriate, visit. Listings will be presented by subject number, treatment group, visit, time point, and parameter as applicable based on all randomized subjects unless otherwise specified.

